15.7 Risk to Benefit Rationale	
APPENDIX I: Abbreviations and Acronyms	
APPENDIX II: Definitions	
APPENDIX V: Monitoring Exposure to Ionizing Radiation	82

APPENDIX VI:	6 Minute Walk Test Guidelines – American Thoracic Society	84
	Monitoring Plan	

(Version 2.0; 01 February 2018)

COMPLIANCE STATEMENT:

This trial will be conducted in accordance with this Protocol/Clinical Investigational Plan, the Declaration of Helsinki, applicable Good Clinical Practices and regulations (e.g., 21 CFR Part 50, 21 CFR Part 56, 21 CFR Part 812, 21 CFR Part 54, 21 CFR Part 11, 45 CFR Part 46, and OUS ISO14155) and the appropriate local legislation(s). The most stringent requirements, guidelines or regulations must always be followed. The conduct of the trial will be approved by the appropriate Institutional Review Board (IRB)/Ethics Committee (EC) of the respective investigational site and by the applicable regulatory authorities.

(Version 2.0; 01 February 2018)

PROTOCOL SUMMARY

PROTOCOL SUMMAR	\				
Trial Name and Number	TRILUMINATE Trial Number #16-517				
Title	Tri al to Eva lu ate Treat m ent with Abbott Transcatheter Clip Repair System in Patients with Moder ate or Greater Tricuspid Regurgitation (TRILUMINATE)				
Objectives	To evaluate performance of the Tricuspid Valve Repair System (TVRS) in patients with symptomatic moderate or greater tricuspid regurgitation who are deemed appropriate for percutaneous transcatheter intervention by the site heart team.				
Intended Use	The Tricuspid Valve Repair System (TVRS) is intended for reconstruction of the insufficient tricuspid valve through tissue approximation.				
Investigational or Trial Device	Tricuspid Valve Repair System (TVRS)				
Targeted number of subjects to receive study device	A minimum of 85 subjects will be enrolled and undergo the TVRS procedure in up to 25 sites				
Clinical Trial/Investigation Design	Prospective, Single Arm, Multi-Center Trial. Patients will be evaluated at baseline, discharge, 30 days, 6 months, 1 year, 2 years, and 3 years				
Primary Effectiveness Endpoint	Echocardiographic Tricuspid Regurgitation (TR) reduction at least 1 grade at 30 days post-procedure, to be tested against a prespecified performance goal.				
Primary Safety Endpoint	A composite of Major Adverse Event (MAE) at 6-months, to be tested against a pre-specified performance goal.				
	 Major Adverse Events (MAE) occurring after femoral vein puncture. MAE as listed below will be adjudicated by the Clinical Events Committee: Cardiovascular Mortality, Myocardial Infarction (MI), Stroke, New onset renal failure, Endocarditis requiring surgery Non-elective Cardio-Vascular (CV) surgery for TVRS device-related AE post-index procedure. 				
Secondary Endpoints	Acute Secondary Endpoints:				

(Version 2.0; 01 February 2018)

Echocardiography Core Laboratory (ECL) assessment of a discharge echocardiogram (30-day echocardiogram will be used if discharge echocardiogram is unavailable or uninterpretable). Subjects who die or undergo tricuspid valve surgery before discharge are an APS failure.

- Acute Device Success: Successful access, delivery of the Clip and removal of device delivery system. Successful delivery of the Clip is the deployment of the device as planned, with no additional unplanned surgery or reintervention related to the device or access procedure.
- Implant Success Rate: Successful delivery and deployment of the Clip(s) with achievement of leaflet approximation(s) and retrieval of the delivery catheter
- Total Procedure Time: defined as the time elapsed from the first of any of the following: intravascular catheter placement or trans-esophageal echocardiogram (TEE), to the removal of the last catheter and TEE
- Device Time: defined as the time the Steerable Guide Catheter is placed in the right atrium until the time the TVRS Delivery System is retracted into the Steerable Guide Catheter
- Fluoroscopy Duration: defined as the duration of exposure to fluoroscopy during the TVRS procedure
- Length of hospital stay for the index TVRS procedure
- Location to which subject was discharged (home, home health or another facility)
 - If subject discharged to another facility, length of stay at facility to which subject was discharged

Clinical Composite Endpoints:

• MAE at discharge, 30 days,1 year, 2 years and 3 years

Clinical Component Endpoints:

Clinical Endpoints at 30 days, 6 months, 1 year, 2 years and 3 years:

- Components of MAE
- All-cause mortality
- NYHA Functional Class
- Tricuspid valve surgery (including type of surgery)
- New use of any cardiac rhythm management devices (Pacemakers, Implantable Cardioverter-Defibrillator (ICD), and Cardiac Resynchronization Therapy (CRT)), including reason for intervention
- Additional TVRS intervention and reason for intervention

(Version 2.0; 01 February 2018)

Additional Clinical Endpoints:

- Major bleeding at 30 days
- Pulmonary Thromboembolism at 30 days
- New Onset Renal Failure at 30 days and 6 months
- New Onset Liver Failure at 30 days and 6 months
- New onset atrial fibrillation at 30 days, 6 months and 1 year.
- Change in diuretic(s) used at 30 days, 6 months, and 1 year (as compared to baseline)

Patient-reported Quality of Life (QoL) and Health Economics and Outcomes Research (HEOR) Endpoints: at Baseline, 30 days, 6 months, 1 year, 2 years and 3 years*:

- Distance walked in the 6-Minute Walk Test (6MWT distance or 6MWD)
- KCCQ QoL scores
- SF-36 QoL scores
- Number and duration of re-hospitalizations and reason for re-hospitalization (i.e., heart failure, cardiovascular, noncardiovascular)
- *Actual rates/scores and the relative change from baseline to each follow-up time point.

Prevalence of Device or Procedure-Related Adverse Events:

Device or procedure-related adverse events will be broken down into those that occur within 30 days of the procedure and those that occur after 30 days of the procedure. Examples of procedure or

device-related adverse events are:Myocardial perforation

- Damage to tricuspid valve apparatus
- Access Site bleeding requiring surgery
- Non-vascular bleeding

Echocardiographic Endpoints

Echocardiographic endpoints will be assessed by the Echocardiography Core Laboratory (ECL) and reported at baseline, discharge, 30 day, 6 months, 1 year, 2 year, and 3 year post-implantation (unless indicated).

	 TR Severity Grade Effective Regurgitant Orifice Area (EROA) Regurgitant Volume Regurgitation Jet Area Vena Contracta Width Proximal Isovelocity Surface Area (PISA) Radius Inferior Caval Vein Diameter Tricuspid Annular Diameters (Antero-Posterior (A-P) and Septal-Lateral (S-P)) Tricuspid Annular area Tricuspid Valve Area Tenting Area (At baseline only) Tenting Distance (At baseline only) Tricuspid Leaflet Tethering Distance (At baseline only) Right Ventricular End Diastolic Dimension (RVEDD) Right Ventricular Fractional Area Change Right Ventricular Systolic Pressure (RVSP) Right Atrial Volume Tricuspid Annular Plane Systolic Excursion (TAPSE) Right Ventricular Free Wall Strain Mean Tricuspid Valve Gradient
	 Forward Stroke Volume (Left Ventricle) Left Ventricular Ejection Fraction (LVEF) Single Leaflet Device Attachment Embolization of the TVRS Clip or TVRS System components Tricuspid Valve Stenosis
Exploratory Endpoints	Hemodynamics through Right Heart Catheterization: Right heart catheter measurements at: Immediately before TVRS procedure: Measurements to include: right atrial a-wave/v-wave, right atrial and ventricular pressures, pulmonary resistance, Pulmonary Artery (PA) pressures and cardiac output), Post-procedure Right Atrial Catheterization, immediately after TVRS procedure (right-atrial a-wave/v-wave, right atrial pressure)
Subject Follow-up	Subjects will have scheduled office visit evaluations at the following time points (Schedule details in Table 2):

[figure not shown]
Key Inclusion Criteria	 Baseline Discharge 30 days 6 months 1 year 2 years 3 years General Inclusion Criteria: Age ≥18 years and ≤90 years at time of consent and must not be a member of a vulnerable population. Subject or a legally authorized representative (where allowed per local regulations; refer to Section 5.1.1) must provide written informed consent prior to any trial related procedure Subject must agree not to participate in any other clinical trial for a period of one year following the index procedure In the judgment of the investigator at the site, subject has been adequately treated per applicable standards (including medical management), including treatment for coronary artery disease, mitral regurgitation and heart failure (e.g., with cardiac resynchronization therapy, revascularization, and/or optimal medical therapy as appropriate; see APPENDIX II: Definitions for definition of optimal therapy) at least 30-days prior to index procedure. The Eligibility Committee must concur that the subject has
	been adequately treated. 5. New York Heart Association (NYHA) Functional Class II (conditional), III, or ambulatory IV a. Subjects with moderate TR: Only NYHA Class III or IV may be considered for inclusion b. Subjects with severe or greater TR: NYHA II, III, or IV may be considered for inclusion
	 6. No indication for left-sided or pulmonary valve correction (Left sided heart valve disease or pulmonary stenosis needs to be adequately treated for at least 30-days prior to study enrollment for TR treatment) 7. The Site Heart Team
	the benefit-risk analysis supports intervention for tricuspid regurgitation per current guidelines for the management of valvular heart disease (refer to Section 5.1.1) and that the subject is at high risk for tricuspid valve surgery. 8. In the judgment of the TVRS implanting Investigator, femoral vein access is determined to be feasible and can accommodate a 25 Fr catheter.

(Version 2.0; 01 February 2018)

Echocardiographic Inclusion Criteria:

9. Moderate or greater (≥2+) Tricuspid Regurgitation determined by the assessment of a qualifying transthoracic echocardiogram (TTE) and transesophageal echocardiogram (TEE) confirmed by the Echocardiography

[figure not shown]
- Tricuspid valve anatomy determined to be suitable for implantation (e.g., no severe leaflet defects preventing proper placement of the TVRS, Ebstein Anomaly) determined by the site heart team
- 11. Tricuspid valve anatomy evaluable by TTE and TEE

Key Exclusion Criteria

General Exclusion Criteria:

- 1. Subject is currently participating in another clinical trial that has not yet completed its primary endpoint.
- 2. Pregnant or nursing subjects and those who plan pregnancy in the period up to 1 year following index procedure. Female subjects of child-bearing potential must have a negative pregnancy test done within 7 days prior to the index procedure per site standard test.
- 3. Severe uncontrolled hypertension Systolic Blood Pressure (SBP) ≥ 180 mmHg and/or Diastolic Blood Pressure (DBP) ≥ 110 mm Hg)
- 4. Systolic Pulmonary Artery Pressure >60mmHg (echo determined)
- 5. Prior tricuspid valve leaflet surgery or any currently implanted prosthetic tricuspid valve, or any prior transcatheter tricuspid valve procedure.
- 6. Mitral Regurgitation moderate-severe or greater severity (≥3+)
- 7. Pacemaker or ICD leads that would prevent appropriate placement of the TVRS Clip
- 8. Active endocarditis or active rheumatic heart disease or leaflets degenerated from rheumatic disease (i.e. noncompliant, perforated).
- 9. MI or known unstable angina within prior 30 days to enrollment
- 10. Percutaneous coronary intervention within prior 30 days to enrollment
- 11. Hemodynamic instability defined as systolic pressure < 90 mmHg with or without afterload reduction, cardiogenic

(Version 2.0; 01 February 2018)

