4.0 ENDPOINTS

4.1 Primary Effectiveness Endpoint

The primary effectiveness endpoint is echocardiographic TR reduction at least 1 grade at 30 days post-procedure, to be tested against a pre-specified performance goal.

(Version 2.0; 01 February 2018)

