4.3 Secondary Endpoints

4.3.1 Acute Secondary Endpoints

- Acute Procedural Success (APS): Successful implantation of the Clip with resulting at least 1 grade reduction in TR severity as determined by the Echocardiography Core Laboratory (ECL) assessment of a discharge echocardiogram (30-day echocardiogram will be used if discharge echocardiogram is unavailable or uninterpretable). Subjects who die or undergo tricuspid valve surgery before discharge are an APS failure.
- Acute Device Success: Successful access, delivery of the Clip and removal of device delivery system. Successful delivery of the Clip is the deployment of the device as planned, with no additional unplanned surgery or re-intervention related to the device or access procedure.
- Implant Success Rate: Successful delivery and deployment of the Clip(s) with achievement of leaflet approximation(s) and retrieval of the delivery catheter.
- Total Procedure Time: Total Procedure Time is defined as the time elapsed from the first of any
 of the following: intravascular catheter placement or trans-esophageal echocardiogram (TEE),
 to the removal of the last catheter and TEE.
- Device Time: Device time is defined as the time the Steerable Guide Catheter is placed in the right atrium until the time the TVRS Delivery System is retracted into the Steerable Guide Catheter.
- Fluoroscopy Duration: Fluoroscopy duration is defined as the duration of exposure to fluoroscopy during the TVRS procedure.
- Length of hospital stay for the index TVRS procedure
- Location to which subject was discharged (home, home health or another facility)
 - If subject discharged to another facility, length of stay at facility to which subject was discharged

TRILUMINATE Trial

(Version 2.0; 01 February 2018)

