5.7 Number of Subjects Required to be Included in the Clinical Investigation

At least 85 subjects will be enrolled and undergo the TVRS procedure to obtain 85 analysis subjects (i.e., subjects who will be included in the analysis of endpoints).

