6.5 Follow-up for All Subjects

Required clinical follow-up will be performed at the following intervals for all subjects with TVRS procedure attempt, regardless of whether a TVRS Clip was successfully implanted:

- Discharge post-TVRS procedure
- 30 days follow-up office visit (this visit must be conducted even if subject is in hospital)
- 6 months
 follow up office visit
- 1 year follow up office visit
- 2 years3 yearsfollow up office visitfollow up office visit
- Discontinuation

Follow-up visits will be calculated from the date of the Procedure. Follow-up assessments can be performed at any point in the window, and should be conducted, whenever possible, by the same individual who performed the baseline tests. The subject should be followed at the investigational site where the subject was enrolled, and may be followed at another investigational site only with prior agreement from that site's Investigator and from the Sponsor.

During the physical examination at the 30-day follow-up clinic visit, the implanting or treating investigator shall examine the integrity of the TVRS Clip. At the 30-day, 6-month, 1-year, 2-year and 3-year follow-up visits, all subjects must be examined by the Investigator. Subjects must continue to take baseline medications without change during follow-up, unless clinically (medically) necessary. If there are any cardiovascular medication changes (including dosage changes), these changes should be documented on the electronic case report form. In general, neurohormonal antagonists should not be changed. Subjects implanted with the TVRS Clip must also be evaluated for device integrity. Required tests and procedures outlined below must be completed. Timing of specific tests will follow the Clinical Evaluation Schedule (**Table 2**) outlined above. All visits and tests must be completed even if the subject is in hospital.

- 12-lead FCG
- Blood draw

(Version 2.0; 01 February 2018)

- Brief physical exam including vital signs (weight, heart rate, blood pressure and temperature)
- Echocardiogram TTE at all follow-up visits and TEE at 30-day visit only
- Modified Rankin Scale (Assessment of mRS should additionally be done at 90 days after onset of stroke)
- 6-Minute Walk Test (6MWT) (excluding discharge and 30-day follow-up visit) See

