1.3.1 Primary Endpoints

The primary effectiveness endpoint is echocardiographic TR reduction at least 1 grade at 30 days post-procedure, to be tested against a pre-specified performance goal.

The primary safety endpoint is a composite endpoint of Major Adverse Event (MAE) at 6-months to be evaluated against a pre-specified performance goal.

MAE is defined as a composite of:

- Cardiovascular Mortality,
- MI,
- Stroke,
- New onset renal failure,
- Endocarditis requiring surgery, and
- Non-elective Cardio-Vascular (CV) surgery for TVRS device-related AE postprocedure.

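### As visibly worded, primary effectiveness success needs only a one-grade TR fall at 30 days, with no condition that a Clip is on the valve or that tricuspid surgery has not intervened

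*Protocol*

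**What the plan says.** The Protocol Summary gives the primary effectiveness endpoint as "Echocardiographic Tricuspid Regurgitation (TR) reduction at least 1 grade at 30 days post-procedure, to be tested against a prespecified performance goal". Protocol 4.1 states: "The primary effectiveness endpoint is echocardiographic TR reduction at least 1 grade at 30 days post-procedure". SAP 1.3.1 carries the same definition, and Protocol 3.2.4 gives TR grading at all visits to the echo core laboratory. SAP 2.2.1.1 adds the PAP, an exact Clopper-Pearson one-sided 97.5% lower limit and a goal of 35%. None of these passages mentions the Clip.

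APS, in Protocol 4.3.1, is built differently. It asks for "Successful implantation of the Clip with resulting at least 1 grade reduction in TR severity", read at discharge, or from the 30-day echo if the discharge echo cannot be used. It also has a failure rule: "Subjects who die or undergo tricuspid valve surgery before discharge are an APS failure". No comparable rule is visible for the primary endpoint.

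Follow-up in Protocol 6.5 is required "for all subjects with TVRS procedure attempt, regardless of whether a TVRS Clip was successfully implanted", with a transthoracic echo at every follow-up visit. Protocol 6.9 keeps subjects in follow-up after tricuspid or mitral valve surgery. Protocol 6.7 allows for an additional TVRS procedure.

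On numbers, Protocol 5.7 says: "At least 85 subjects will be enrolled and undergo the TVRS procedure to obtain 85 analysis subjects". The PAP is defined in SAP 1.4, whose content is not readable in the public text.

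**The concern.** The trial has a single arm, so the comparison with 35% is the only evidence on effectiveness that is formally tested. A one-grade fall can also come from a change in diuretics, from loading conditions or from variation in grading. It can come from tricuspid surgery as well. In a subject with no Clip on the valve, or one operated on before day 30, the fall is not the work of the device, yet the visible rule scores it as a success.

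The missing-data rule in SAP 2.4 does not deal with this. It excludes missing data, whereas these subjects may have a readable 30-day echo.

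What is at stake is the meaning of the success rate. A reader will take it as the share of patients in whom the device reduced TR.

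**Working it through.** **Inputs from the documents.** N = 85 (Protocol 5.7); goal 35% and exact one-sided 97.5% lower limit (SAP 2.2.1.1); overall type I error 2.5% (SAP 2.6).

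**Inputs assumed.** The documents do not give the share n of attempts that leave no Clip, or the share s of those subjects whose grade falls anyway. I take n = 2-10% and s = 10-30%.

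**Step 1: the decision rule.** The trial passes if the Clopper-Pearson lower limit exceeds 0.35.
- 38/85 = 44.7%: lower limit 0.3391, fails.
- 39/85 = 45.9%: lower limit 0.3502, passes.
- Size: P(X ≥ 39 | N = 85, p = 0.35) = 2.48%, consistent with the stated 2.5%.

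**Step 2: number of subjects affected.** Extra successes = 85 × n × s.
- Low: 85 × 0.02 × 0.10 = 0.17 subjects (0.2 percentage points).
- Middle: 85 × 0.05 × 0.20 = 0.85 subjects (1.0 point).
- High: 85 × 0.10 × 0.30 = 2.55 subjects (3.0 points).

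**Step 3: chance of passing, which depends on the null.**

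*Null A: device-attributable success is 35% of all attempts.* No-Clip improvers come on top, so p = 0.35 + n × s.
- p = 0.352: 2.7%.
- p = 0.360: 3.9%.
- p = 0.380: 8.4%.

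Under this null, Clip subjects succeed at 0.35/(1 − n), which is 35.7% at n = 2% and 38.9% at n = 10%.

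*Null B: subjects with a Clip succeed at exactly 35%.* Then p = (1 − n) × 0.35 + n × s.
- n = 2%, s = 10%: p = 0.3450, chance 1.96%.
- n = 5%, s = 20%: p = 0.3425, chance 1.73%.
- n = 10%, s = 30%: p = 0.3450, chance 1.96%.
- Other corners: n = 2%, s = 30% gives p = 0.3490 and 2.37%; n = 10%, s = 10% gives p = 0.3250 and 0.69%.

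All are below 2.48%, because every assumed s is below the 35% goal. The chance exceeds 2.48% only if no-Clip subjects improve more often than 35%. For example, with s = 50% it is 3.4% for 4 no-Clip subjects and 4.9% for 9.

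**Step 4: what the failure rule costs in power.** Assume Clip subjects succeed at 50% and s = 20%.
- 4 of 85 with no Clip: chance of passing 73.0% as worded, 67.2% if no Clip means failure.
- 9 of 85 with no Clip: 61.3% against 45.4%.

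Embolised Clips and early tricuspid surgery are not in these figures, since the documents give no rates for them.

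**The case against.** The strongest objection is that membership of the primary analysis is set by the PAP, whose definition is redacted and so cannot be called absent. The PAP may be limited to implanted subjects, or may already class these cases. Protocol 5.7 does not settle the matter: it says how many will undergo the procedure in order to reach 85 analysis subjects, not that every attempt is analysed. The Protocol Summary describes the same 85 as the target number to receive the device. Protocol 6.5 governs visits, not analysis membership. This stands, and it limits the point to the visible wording. A PAP restricted to implanted subjects would still leave a Clip that later embolised, or early surgery, to be classed.

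A reader might go further and infer that any success without a Clip breaks the 2.5% error control. The documents do not support that. Type I error is defined against the endpoint as written, and the exact test has size 2.48% for it whatever the Clip status. The 2.7-8.4% belongs to a different null (Null A). Under Null B, keeping failed attempts in the denominator is conservative within the assumed range.

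It is also fair to say that APS is a different, acute endpoint, and that Implant Success and Acute Device Success will be reported separately, so failed placements will be seen. That makes the difference from APS a design choice and not a contradiction. It does not tell the reader how those subjects are scored in the primary test.

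**Conclusion.** The point holds as a gap in the visible definition: nothing shown prevents a PAP subject with no Clip on the valve, or with earlier tricuspid surgery, from scoring as a primary effectiveness success. It is not established that such subjects are in the PAP, and the plan's type I error claim is not shown to fail.

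The likely size is small, about 0.2-2.6 of 85 subjects, and rests wholly on the assumed n and s. It would matter mainly for a result close to the 39/85 pass mark, and for how the success rate is interpreted.

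**What to change.** In Protocol 4.1 and SAP 2.2.1.1, state that PAP subjects with no Clip attached to the tricuspid valve at the 30-day echo, or with tricuspid valve surgery before that echo, count as failures and stay in the denominator. State also how a subject whose Clip was placed at an additional TVRS procedure before day 30 is classed. A condition tied to the index procedure alone would leave that case unclear. Wording the rule as no Clip attached, and not as any Clip embolised, avoids failing a subject with several Clips because one was lost.

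The cost is a sentence or two in each document. Implant, embolization and surgery data are already collected. The success rate may be slightly less favourable, with some loss of power if many attempts leave no Clip. If the PAP definition already handles these subjects, the text only confirms it and does no harm.

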4.2 Primary Safety Endpoint

The primary safety endpoint is a composite of Major Adverse Event (MAE) at 6-months to be evaluated against a pre-specified performance goal.

MAE is defined as a composite of:

- Cardiovascular Mortality,
- MI.
- Stroke,
- New onset renal failure,
- · Endocarditis requiring surgery, and
- Non-elective CV surgery for TVRS device-related AE post-procedure.

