5.3 Subject Enrollment

Subjects are enrolled in the TRILUMINATE Trial upon signing and dating the informed consent form.

^{*} For Switzerland Only: A legally authorized representative will not be allowed to provide informed consent for a patient.

³⁰ Braun D, Nabauer M, Orban M, Orban M, Gross L, Englmaier A, Rösler D, Mehilli J, Bauer A, Hagl C, Massberg S, Hausleiter J. Transcatheter treatment of severe tricuspid regurgitation using the edge-to-edge repair technique. EuroIntervention, 2017 Feb 3:12(15):e1837-e1844.

³¹ Nickenig G, Kowalski M, Hausleiter J, Braun D, Schofer J, Yzeiraj E, Rudolph V, Friedrichs K, Maisano F, Taramasso M, Fam NP, Bianchi G, Bedogni F, Denti P, Alfieri O, Latib A, Colombo A, Hammerstingl C, Schueler R. Transcatheter Treatment of Severe Tricuspid Regurgitation with the Edge-to-Edge: MitraClip Technique. Circulation. 2017 Mar 23.

(Version 2.0; 01 February 2018)

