B. Subject has clinical signs and/or symptoms of heart failure, including new or worsening dyspnea, orthopnea, paroxysmal nocturnal dyspnea, increasing fatigue, worsening functional capacity or activity intolerance, or signs and/or symptoms of volume overload,

AND

Abbott Vascular

TRILUMINATE Trial

(Version 2.0; 01 February 2018)

C. Results in intravenous (e.g., diuretic or vasoactive therapy) or invasive (e.g., ultrafiltration, IABP, mechanical assistance) treatment for heart failure.

For the purpose of this protocol, overnight stays at nursing home facilities, physical rehab or extended care facilities, including hospice, do not meet the protocol definition of hospitalization.

OTHER CARDIOVASCULAR HOSPITALIZATION

Defined as treatment in any inpatient unit or ward in the hospital for at least 24 hours, including emergency department stay for conditions such as coronary artery disease, acute myocardial infarction, hypertension, cardiac arrhythmias, cardiomegaly, pericardial effusion, atherosclerosis and peripheral vascular disease, not related to heart failure as defined.

NON-CARDIOVASCULAR HOSPITALIZATION

Hospitalizations that are not heart failure or other cardiovascular hospitalizations, as defined above, will be categorized as non-cardiovascular hospitalizations.

LIVER FAILURE

New onset liver failure is defined as elevated alanine aminotransferase (ALT) or aspartate aminotransferase (AST) greater than 15 times the ULN.

MAJOR ADVERSE EVENT (MAE)

MAE is a CEC-adjudicated composite of cardiovascular mortality, stroke, myocardial infarction, new onset renal failure, endocarditis requiring surgery, and non-elective cardiovascular surgery for TVRS device related adverse events occurring after the index procedure

MAJOR BLEEDING

Major bleeding is defined as bleeding \geq Type 3 based on a modified Bleeding Academic Research Consortium (BARC)³³ definition:

- Type 3
 - Type 3a
 - Overt bleeding plus hemoglobin drop of 3 to <5 g/dL* (provided hemoglobin drop is related to bleed)
 - Any transfusion with overt bleeding
 - o Type 3b
 - Overt bleeding plus hemoglobin drop ≥5 g/dL* (provided hemoglobin drop is related to bleed)
 - Cardiac tamponade
 - Bleeding requiring surgical intervention for control (excluding dental/nasal/skin/hemorrhoid)
 - Bleeding requiring intravenous vasoactive agents
 - o Type 3c
 - Intracranial hemorrhage (does not include microbleeds or hemorrhagic transformation, does include intraspinal)

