Cardiovascular surgical procedure performed for device related complication requiring surgery within 24 hours of onset of adverse event, including events found during scheduled follow-up. If non-urgent surgery was performed within 24 hours of the onset of the adverse event but was not required within this timeframe, it will not be considered "non-elective". Examples of Device Related Complications that may

(Version 2.0; 01 February 2018)

lead to non-elective cardiovascular surgery include, myocardial perforation, Single Leaflet Device Attachment (confirmed by Echo Core Lab), embolization of the TVRS Clip or TVRS System components, iatrogenic atrial septal defect, or the need for tricuspid valve replacement instead of repair due at least in part to the TVRS procedure or the presence of the TVRS Clip.

OPTIMAL MEDICAL THERAPY OR OPTIMAL THERAPY

For Tricuspid Regurgitation: Currently per ESC 2012 guidelines, the only medical therapy described is, "Diuretics reduce congestion. Specific therapy of the underlying disease is warranted." These TR patients typically would have some level of left heart failure by the time TR is detected. Hence, optimal therapy for TR at the present time will follow that defined for patients with left heart failure issues, example mitral regurgitation.

For Mitral Regurgitation: Subjects with current or prior symptoms of heart failure and reduced LVEF should be on stable optimally uptitrated medical therapy recommended according to current guidelines (J Am Coll Cardiol. 2013 Jun 5. doi:pii: S0735-1097(13)02114-1.) as standard of care for heart failure therapy in the United States. This minimally includes an ACE-inhibitor (ACE-I) at stable doses for 30 days prior to subject enrollment in the trial, if tolerated, and a beta blocker (carvedilol, sustained release metoprolol succinate, or bisoprolol) for 90 days prior to subject enrollment in the trial, if tolerated, with a stable up-titrated dose for 30 days prior to subject enrollment in the trial. This also includes an Angiotensin II Receptor Blocker (ARB) at stable doses for 30 days prior to subject enrollment in the trial, if tolerated, when ACE-I is not tolerated. Stable is defined as no more than a 100% increase or a 50% decrease in dose.

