2.1.2 Descriptive Statistics for Categorical Variables

For categorical variables such as gender, MAE, results will be summarized with subject counts and percentages/rates, and where specified in the table mockups, with exact 95% Clopper-Pearson⁸ confidence intervals.

For effectiveness and safety endpoint(s), relative risks (i.e., the ratio of rates), confidence interval for the relative risks, the difference in rates and the confidence interval for difference in rates (using previously-described formulas), and p-values may also be presented for hypothesis generating purposes.

For the determination of event rates at time points (e.g. 30 days), the counting starts from the time of enrollment.

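### SAP 2.1.2 starts event-rate counting at enrollment (signed consent), while the rest of the plan runs from the procedure, and the Kaplan-Meier text for the 6-month MAE test names no time origin

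*Protocol*

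**What the plan says.** Two starting points appear in the documents.

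**Consent.** SAP 2.1.2, which names MAE among its categorical variables, says of event rates at time points that "the counting starts from the time of enrollment"; its example is 30 days. Protocol 5.3 says "Subjects are enrolled in the TRILUMINATE Trial upon signing and dating the informed consent form", and Protocol 3.1 also ties enrollment to signed consent, for eligible subjects.

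**Procedure.**
- The Protocol Summary (Primary Safety Endpoint) counts "Major Adverse Events (MAE) occurring after femoral vein puncture".
- Protocol 6.5 calculates follow-up visits from the procedure date.
- SAP 1.3.1 sets the primary effectiveness endpoint at 30 days after the procedure.
- SAP 1.3.2.5 splits device- or procedure-related adverse events at 30 days from the procedure.
- SAP 1.3 times the extra 4- and 5-year US follow-up from the procedure.

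**No origin stated.** SAP 2.1.4 sends clinical events beyond 30 days to Kaplan-Meier. SAP 2.2.1.2 applies Kaplan-Meier with Greenwood limits to the 6-month MAE rate and tests it against 39%. Neither visible section says when time starts.

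**The concern.** Consent and puncture cannot coincide under this protocol. Consent is required before any data go to the echo core laboratory (Protocol 5.2.1), and the procedure may be scheduled only after the Eligibility Committee confirms eligibility (Protocol 3.0). A clock started at consent therefore includes time before the subject has been exposed to the device.

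The 30-day MAE rate is a secondary endpoint, and 30-day event rates are the example that SAP 2.1.2 gives, so the sentence reaches that rate directly. The larger stake is the 6-month MAE rate. This is a single-arm trial judged against a fixed goal, so there is no control arm in which the same shift would occur and cancel. A programmer who looks in the visible SAP for a time zero finds only the one in 2.1.2.

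**Working it through.** The plan gives no figure that depends on the time origin, so there is none to reproduce. The check has three steps.

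**1. Window covered.** Let L be the days from consent to puncture. A rate at T days from consent covers T − L days after puncture. The documents give no value for L, so 14 and 30 days are assumed.

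| Rate | L = 14 | L = 30 |
|---|---|---|
| 30 days | 16 days after puncture | 0 days |
| 6 months (taken as 180 days) | 166 days | 150 days |

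**2. Pass line for the safety test.** Inputs: 85 analysed (Protocol 5.7), goal 39% (SAP 2.2.1.2) and no censoring (assumed). A one-sided 97.5% limit is also assumed: SAP 2.6 gives 2.5% overall and SAP 2.2.1.1 uses that limit for effectiveness, but SAP 2.2.1.2 does not restate it. Without censoring, the linear Greenwood upper limit is p + 1.96 × √(p(1 − p)/85).

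- 24/85 = 28.2%: 0.2824 + 1.96 × √(0.2824 × 0.7176/85) = 0.378, passes.
- 25/85 = 29.4%: 0.2941 + 1.96 × √(0.2941 × 0.7059/85) = 0.391, fails.

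SAP 2.2.1.2 does not say which form of Greenwood limit is meant. With log-log or exact limits the last passing count is 23/85 = 27.1% (upper limits 37.9% and 37.8%), and 24/85 fails (39.1% and 39.0%). So 25/85 fails under all three.

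**3. The same result counted from consent.** Take R = 25/85 = 0.2941 at 180 days from puncture, and assume that no MAE is counted before puncture.

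- *Constant hazard:* 1 − (1 − R)^((180 − L)/180).
  - L = 14: 1 − 0.7059^(166/180) = 0.2747
  - L = 30: 1 − 0.7059^(150/180) = 0.2519
- *Front-loaded:* three quarters of the events by day 30, constant hazard afterwards. Event-free at day 30: 1 − 0.75 × 0.2941 = 0.7794. Event-free from day 30 to day 180: 0.7059/0.7794 = 0.9057. Rate: 1 − 0.7794 × 0.9057^((150 − L)/150).
  - L = 14: 1 − 0.7794 × 0.9057^(136/150) = 0.2876
  - L = 30: 1 − 0.7794 × 0.9057^(120/150) = 0.2800

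| Assumed lag | Front-loaded | Constant hazard | Fall from 29.4% |
|---|---|---|---|
| 14 days | 28.8% | 27.5% | 0.7 to 1.9 points |
| 30 days | 28.0% | 25.2% | 1.4 to 4.2 points |

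These are average readings, not attainable counts. Set against the pass lines, 25.2% lies below all of them, 28.0% and 27.5% lie below the linear line only (28.2%), and 28.8% lies below none.

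**The case against.** **The sentence may not govern the primary test.** It stands in the descriptive section for categorical data, with a 30-day example, and the 6-month MAE rate goes to Kaplan-Meier. Other SAP text points to the procedure, including SAP 2.1.5, which divides follow-up time at the index procedure. SAP 1.4, on analysis populations, is not visible and could hold a time zero. All of this stands: applying the enrollment origin to the 39% test is an inference. It does not rescue the sentence itself, which conflicts with the rest of the plan for 30-day rates.

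**Enrollment may come later than consent.** Protocol 11.8.4 has the Eligibility Committee decide whether a patient can be enrolled. That reading shortens the lag but does not remove it, because scheduling follows the committee's confirmation.

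**The direction is not fixed.** A reader might infer that the enrollment clock must favour the device. That needs the puncture rule as a filter. The MAE definition in SAP 1.3.1 has no such filter, and Protocol 7.3.1 collects adverse events from enrollment. If pre-puncture events also count, they offset the late events that are lost, and the net effect is unknown.

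**Surgery during the index procedure.** A reader might also infer that the puncture rule makes such surgery an MAE, and that the surgery component contradicts it. The documents do not support this. The listings agree on a post-procedure limit: "surgery for TVRS device-related AE post-index procedure" in the Protocol Summary, "Non-elective CV surgery for TVRS device-related AE post-procedure" in Protocol 4.2, "non-elective cardiovascular surgery for TVRS device related adverse events occurring after the index procedure" in Appendix II and "surgery for TVRS device-related AE postprocedure" in SAP 1.3.1. A narrower limit on one component inside a general window is not a contradiction. The separate Appendix II entry ("Cardiovascular surgical procedure performed for device related complication requiring surgery within 24 hours of onset of adverse event") defines non-elective surgery; it does not set the MAE window. Whether the limit attaches to the surgery or to the adverse event could be worded more clearly, and no more than that follows.

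**Conclusion.** SAP 2.1.2 is wrong as written. Its enrollment origin conflicts with the puncture and procedure origins used elsewhere, and it shortens the post-procedure window of a 30-day event rate by the whole interval from consent to puncture.

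For the 6-month MAE test the point is conditional. The visible SAP states no other origin, so the same shortening would follow if the sentence is applied. With assumed lags of 14 to 30 days, and only post-puncture events counted, a 29.4% rate would fall by 0.7 to 4.2 points. That can move a result lying just beyond the pass line. The figures rest on 85 subjects without censoring, a one-sided 97.5% limit and two assumed hazard shapes. They do not show that the planned test is biased. The primary effectiveness endpoint is unaffected, because its own definition runs from the procedure.

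**What to change.** - In SAP 2.1.2, replace enrollment with the index procedure, defined as femoral vein puncture as in the Protocol Summary.
- In SAP 2.2.1.2, state the same origin for the 6-month Kaplan-Meier analysis.
- Carry the rule that MAE count from femoral vein puncture into Protocol 4.2, the Appendix II definition of MAE and SAP 1.3.1.
- Optionally, clarify what the post-procedure limit on the surgery component attaches to, consistently with the definition behind the 39% goal. No change to which surgery counts is proposed.

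The cost is a few sentences in the protocol and SAP. No new data are needed. The reported MAE rate may be slightly less favourable than one counted from consent.
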